The benefits of cannabis may be offset by its adverse events.²⁷ Cannabis is linked to psychological symptoms including anxiety, depression,²⁸ and psychotic symptoms.²⁹ In some studies, cannabis use is associated with poor ARV adherence and virologic failure;³⁰ in others, this is not the case.³¹ No studies have examined how THC/CBD content contributes to adverse events (psychological symptoms, poor ARV adherence, and virologic failure).

Our overarching goal is to test how medical cannabis use affects neuropathic pain, with particular attention to THC/CBD content and adverse events. We propose an observational cohort study of 100 PLWH with (a) neuropathic pain, (b) active certification for medical cannabis, and (c) intent of being dispensed soft-gel capsule products at a medical cannabis dispensary (including high THC: low CBD product and high CBD:low THC product). Over 14 weeks, participants will have 2 in-person visits and 15 phone-based questionnaires (one at baseline, and every week for 14 weeks). Data sources will be blood and urine samples, questionnaires, and medical and pharmacy records. The primary independent variable will be the type of soft-gel capsule product. The secondary independent variable will be reported cumulative THC and CBD dose. The primary outcome will be self-reported pain severity.³² Secondary outcomes will be pro-inflammatory cytokines (TNF α , IL-6), anti-inflammatory cytokines (IL-4, IL-10),¹⁵ psychological symptoms (symptoms of depression,³³ anxiety,³⁴ and psychosis³⁵), ARV adherence, and VL. Among PLWH with neuropathic pain, we will:

Aim 1: Examine how medical cannabis use affects self-reported pain. *H1:* The effect of medical cannabis use on self-reported pain-severity will differ by THC/CBD content.

Aim 2: Examine how medical cannabis use affects pro- and anti-inflammatory cytokines.

H2: Medical cannabis that has higher THC content will have greater reduction in pro-inflammatory cytokines (TNF α , IL-6). *H3:* Medical cannabis that has higher CBD content will have greater increase in anti-inflammatory cytokines (IL-4, IL-10).

Aim 3: Examine how medical cannabis use affects adverse events. *H4:* Participants who use high THC (vs. high CBD) cannabis products will have more psychological symptoms, poorer ARV adherence, and less suppressed VL.

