In-person visits: Participant's 2 in-person visits will occur in private rooms at the Montefiore/Einstein ICTR Clinical Research Center. At the baseline visit, study staff will describe the study and obtain written informed consent. Tracking forms as well as agreements to release medical, pharmacy, and PMP records will be completed. Participants will receive a refillable debit card for compensation. At all in-person visits, we will administer questionnaires, and collect blood and urine samples. Participants will receive \$27.50 for each in-person visit.

Phone or web visits will occur weekly over 14 weeks and include brief (5-7 minute) questionnaires administered by study staff over the phone or completed on-line. A total of 15 visits will occur, the first at baseline, when participants can be trained on how to complete it, and then one at the end of each week of the follow-up period. Participants will receive \$3 on debit cards after completing each phone or web-based questionnaire.

Blood draws will occur at week 0 and 14 in-person visits. They will measure VL, CD4 count, pro- and anti-inflammatory cytokines. Participants will be compensated an additional \$15 for each visit in which there is a blood draw.

Main independent variable will be the soft gel capsule product dispensed at Vireo, including a 1) high THC capsule, or 2) high CBD capsule. Other key independent variables will be cumulative THC and CBD taken (weeks 3-14, continuous measures).

Main outcome variables: Our primary outcome is pain severity, measured via the BPI severity scale (ordinal variable), as recommended by a committee of international pain experts.⁹² It is an 11-point (0-10) numerical rating scale of pain intensity, where 0 is 'No pain' and 10 is 'Pain as

bad as you can imagine'. Participants will complete the BPI severity scale in each phone visit (baseline and at each weekly visit).

Pro- (TNF α , IL-1 β , IL-6) and *anti-* (IL-4, IL-10) *inflammatory cytokines (secondary outcomes;* 0, 14 week *blood draws*) will be measured with Luminex assay and reported as picograms per mm 3 (continuous measure).

Adverse events (secondary outcomes) will be ARV adherence (AIDS Clinical Trial Group [ACTG] Adherence Interview,^{93,108} Adherence Visual Analog Scale [VAS; weekly]),⁹⁴ VL suppression (blood draws at 0, 14 weeks; copies/mL); and psychological symptoms—depression (CES-D; 0 and 14 weeks),⁹⁵ anxiety (GAD-7; 0 and 14 weeks),^{96,94,97,109}

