Aim 1: Examine how medical cannabis use affects self-reported pain. H1: The effect of medical cannabis use on self-reported pain-severity will differ by THC/CBD content. The primary outcome will be change in BPI pain severity scale (ordinal variable, 0-10; measured at baseline and weekly for 14 weeks). A clinically significant change is 30% reduction in BPI pain severity scale.⁹² Secondary measures will include BPI pain interference scale and neuropathic pain (painDETECT). We will compare the proportion of participants who achieve clinically significant change in pain at 14 weeks between those who use high THC soft gel capsules and those who use high CBD soft gel capsules. BPI pain interference scale and painDETECT will be compared between those using high THC vs high CBD as well. We will use mixed-effects logistic regression to test the effect of study arm on pain relief across the course of the study. Results will be adjusted for covariates associated with the outcomes of interest on bivariate testing. We will repeat this model using alternative measures of medical cannabis (cumulative dose of THC and CBD).

Aim 2: Examine how medical cannabis use affects pro- and anti-inflammatory cytokines. H2: Medical cannabis that has higher THC content will have greater reduction in pro-inflammatory

cytokines ($TNF\alpha$, $IL-6$). *H3: Medical cannabis that has higher CBD content will have greater increase in anti-inflammatory cytokines ($IL-4$, $IL-10$).* We will examine how pro- and anti-inflammatory cytokines measured at 0 and 14 weeks change in participants using high THC products versus high CBD products. We will use mixed-effects linear regression analyses to examine intervention and time effects as well as intervention-by-time interactions. This approach is appropriate in the event that the pro- and anti-inflammatory cytokine data show a non-normal distribution. We will repeat this model using alternative measures of medical cannabis (cumulative dose of THC and CBD). We will adjust for other chronic conditions that may lead to change in inflammatory cytokines, such as obesity, cardiovascular disease, and diabetes.

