Aim 3: Examine how medical cannabis use affects adverse events. *H4: Participants who use high THC (vs. high CBD) cannabis products will have more psychological symptoms, poorer ARV adherence, and less suppressed VL.* We will examine whether participants using high THC products vs high CBD products have a greater chance of adverse events, including psychological symptoms, ARV adherence, and VL. We will use mixed-effects linear regression analysis for continuous measures (VL, ARV adherence, and psychological symptoms). Each adverse event (Table 8) will be included in a separate model. We will repeat this model using alternative measures of medical cannabis (cumulative dose of THC and CBD).

Aim 4: Explore mechanisms by which medical cannabis promotes analgesia. *H5: Different doses of THC and CBD will have differing effects on inflammatory cytokines, psychological symptoms, and ultimately analgesia.*

We will use a pooled analysis of THC and CBD, using weekly questionnaires and PMP records. We will examine these relationships longitudinally in a stepwise process. First, we will conduct a mixed-effects model to examine how potential mediators lead to analgesia (reduction in BPI severity score). We will repeat analyses for possible mediators, including inflammatory cytokines and psychological symptoms. We will also determine if exposures influence changes in these variables over time, which in turn, influence change in analgesia (e.g., using time-lagged mediators and outcomes). Mediators found to be significant will be included in the final model.⁹² We will calculate the standardized total effect from the exposures to analgesia as well as the standardized mediational (i.e., indirect) effects via mediators. The mediational effect is calculated as the product of the effect from the exposures to the mediators, and the effect from the mediators to the outcome.

8) Data quality control and database management

Data management: Questionnaire, medical records, and PMP data will be de-identified and entered by study staff into a password-protected computer and database. Paper records will be stored in a locked filing cabinet that only research staff can access. Medical and PMP record data will be de-identified and entered in a secure HIPAA compliant web-based system. To protect confidentiality, we will use separate processes for ID- and name-based files and seek a certificate of confidentiality.

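### The weeks 3-14 cumulative dose has no defined time structure in the weekly Aim 1 pain model, so dose is not placed before the pain ratings it is meant to explain

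*Combined protocol and SAP*

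**What the plan says.** All references are to the combined protocol and SAP.

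- **Status of dose.** Section 1.A: "The secondary independent variable will be reported cumulative THC and CBD dose". Product type is the primary independent variable.
- **Definition.** Section 2.C, main independent variable: "cumulative THC and CBD taken (weeks 3-14, continuous measures".
- **Outcome schedule.** Section 2.C: "Participants will complete the BPI severity scale in each phone visit (baseline and at each weekly visit". The weekly contacts fall "one at the end of each week of the follow-up period".
- **Model.** Section 7.A, Aim 1: "We will use mixed-effects logistic regression to test the effect of study arm on pain relief across the course of the study". The dose version follows: "We will repeat this model using alternative measures of medical cannabis (cumulative dose of THC and CBD". Aims 2 and 3 carry the same instruction.
- **Single-time comparison.** Section 7.A, Aim 1 also states, by product: "We will compare the proportion of participants who achieve clinically significant change in pain at 14 weeks".
- **Dose data.** Section 7.A, Aim 4 builds pooled dose "using weekly questionnaires and PMP records". Section 3.C lists THC and CBD dose taken among the questionnaire topics.

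No section says whether cumulative dose is a single sum per participant or is updated at each rating. None says how weeks 1 and 2 enter the dose model. Time lags appear only under Aim 4, as an example, and for mediators and outcomes rather than for dose in Aim 1.

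**The concern.** The exposure window (weeks 3-14) and the outcome span (weeks 1-14) do not match. The study is observational: it assigns no dose, and participants decide how much to take. Someone whose pain persists may take more, and someone who gets no relief may stop. Either way, pain affects dose as well as the reverse.

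A dose variable that includes intake after a rating, or in the same week as it, can therefore be associated with relief even if dose does nothing. What is at stake is the dose-response reading of Aim 1, which rests on the named secondary exposure. Aim 4 also takes pooled dose as its exposure.

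**Working it through.** **1. Does the Aim 1 model use many weekly ratings?** Section 3.A and Table 9 state power of 0.84 for 40% against 20% responders, with 42 per arm, ICC 0.4 and a two-sided 5% level. Take m = 14 ratings and an effective n per arm of 42 / [(1 + (m − 1) × ICC) / m].

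- ICC 0.4: 42 / (6.2 / 14) = 94.8, power 0.858 (stated 0.84)
- ICC 0.3: 42 / (4.9 / 14) = 120.0, power 0.927 (stated 0.91)
- ICC 0.2: 42 / (3.6 / 14) = 163.3, power 0.979 (stated 0.97)
- One time point, 42 per arm: power 0.516

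The stated power needs repeated ratings. It cannot tell 14 from 12 (m = 12 gives 0.852 at ICC 0.4), so the span of weeks 1-14 rests on the text of Sections 2.C and 7.A.

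**2. Fixed-total reading.** Ratings come at the end of each week, so dose in week w precedes rating w. Only dose weeks later than w count as after the outcome. Out of 12 dose weeks, the number that come later is:

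| Rating week | 1 | 2 | 3 | 4 | 5 | 6 | 7 | 8 | 9 | 10 | 11 | 12 | 13 | 14 |
|---|---|---|---|---|---|---|---|---|---|---|---|---|---|---|
| Later dose weeks | 12 | 12 | 11 | 10 | 9 | 8 | 7 | 6 | 5 | 4 | 3 | 2 | 1 | 0 |

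The sum is 90 of 14 × 12 = 168, or 53.6%. The later share exceeds half only for weeks 1-7.

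**3. Sensitivity to the dose pattern.** The documents give no weekly pattern, so these are assumptions. A dose in week e is later than e − 1 of the 14 ratings. The share is therefore Σ d(e) × (e − 1) / [14 × Σ d(e)], summed over e = 3 to 14.

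- Equal: 90 / (14 × 12) = 53.6%
- Rising linearly to double: 148 / (14 × 18) = 58.7%
- Falling linearly to half: 61 / (14 × 9) = 48.4%
- Use stops after week 12: 65 / (14 × 10) = 46.4%
- Use stops after week 10: 44 / (14 × 8) = 39.3%

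Steeper patterns go slightly further: 32 / (14 × 6) = 38.1% for a linear fall to zero, and 264 / (14 × 30) = 62.9% for a fourfold rise. With ratings limited to weeks 3-14 and equal dosing, the share is 66/144 = 45.8%. For a week-14 outcome it is 0%.

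**4. Running-sum reading.** No dose follows the rating (0%). The sum starts at week 3, so everyone has zero exposure at weeks 1 and 2. The current week's dose is included, so same-week feedback remains.

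**5. Can feedback alone produce a dose effect?** Two sets of null simulations were run (84 participants, 14 weeks, dose has no effect, cluster-robust linear probability model). Intake drifts by 1% or 2% per week for each BPI point above the response threshold. Drift, dose spread, baseline BPI and variances are assumptions. False-positive rates at ICC 0.4:

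| Exposure | 1% drift | 2% drift |
|---|---|---|
| Set A (300 replicates, log-dose SD 0.5 and 0.3) | | |
| Fixed weeks 3-14 total | 40-77% | 90-100% |
| Running sum from week 3 | 24-48% | 57-91% |
| Lagged mean dose, unadjusted | 13-19% | 25-53% |
| Lagged mean dose, adjusted for prior pain | 8-9% | 7-12% |
| Set B (600 replicates, log-dose SD 0.25, 0.5, 0.75) | | |
| Fixed weeks 3-14 total | 89%, 40%, 26% | not reported |
| Mean dose, adjusted for mean prior BPI | 8-24% | 10-48% |

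With no drift, all four Set A models gave 5-8%. At ICC 0.2 the Set A fixed total gave 28-52% and 65-97%.

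**The case against.** The strongest reply is that the sponsor may intend a running sum. Dose is collected weekly, so one can be built, and then no exposure follows the outcome. This stands as far as it goes. A reader might infer from the closed window that the plan specifies a fixed total, so that more than half of the exposure falls after the outcome. The documents do not support that: they are silent on the form, and even for a fixed total the share drops below half if use declines or stops early. The running sum does not settle the matter, because weeks 1 and 2 still lack exposure and dose is still unlagged.

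Three other stronger readings also fail.

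- A single false-positive rate cannot be quoted. The rate moves widely with the assumed dose spread, and the simulated model is not the planned mixed-effects logistic model.
- The bias need not run towards higher dose with worse pain. That sign follows from the drift rule, and non-responders who stop would reverse it.
- The main result is not at risk, since the Aim 1 product comparison does not use dose.

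It is also fair to say that Aim 4 already plans longitudinal work with time lags, although not explicitly for dose.

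**Conclusion.** The concern holds in a conditional form. The plan leaves the time structure of cumulative dose undefined in a model whose ratings begin two weeks before the dose window. The size depends on the reading: about 54% of exposure weeks follow the outcome for a fixed total with equal dosing and equal weight on 14 ratings, and none do for a running sum. Both readings inflated false positives when pain was allowed to drive intake, and the running sum did so less. That feedback is plausible where intake is self-chosen, but the documents do not quantify it, so the simulations show vulnerability rather than an expected error rate. This is worth correcting before analysis, as a point about the secondary dose models only.

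**What to change.** In Sections 2.C and 7.A, state the following.

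1. For weekly pain models, exposure is cumulative or mean THC and CBD taken from the start of use, including weeks 1 and 2, up to the week before each BPI rating. The model adjusts for baseline BPI.
2. The weeks 3-14 total is used only for outcomes measured at week 14, such as cytokines, VL, CES-D and GAD-7.
3. A sensitivity analysis also adjusts for the prior-week BPI. Earlier pain may lie on the path from earlier dose to later pain, so this may remove part of the effect being estimated.

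The cost is SAP wording and a little programming, since weekly dose and weekly BPI are already collected. Week 1 has no lagged dose and drops out of this secondary model. Lagging reduces the feedback problem but does not remove it: unadjusted lagged dose still gave 13-19% at 1% drift, and the version adjusted only for baseline BPI was not simulated. The dose results should be reported as associations.

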Aims 1-4	Medical cannabis use	Initial soft-gel capsule dispensed at Vireo Certification for medical cannabis (date, doctor, conditions) All medical cannabis products dispensed (date, product, dose, amount dispensed) Self-reported medical and unregulated cannabis use (product, # of days used, route, dollar amount of unregulated cannabis purchased, ASI)	PR MR PR TQ
Primary outcome variables			
Aims 1, 4	Pain Severity	Brief Pain Inventory (BPI) Severity subscale ⁹⁰	TQ
Secondary outcome variable			
Aims 2, 4	Inflammatory cytokines	Pro-inflammatory cytokines (TNF α , IL-6) Anti-inflammatory cytokines (IL-4, IL-10)	B B
Aims 3, 4	Adverse events	VL, CD4 count AIDS Clinical Trial Group (ACTG Adherence) ⁹³ , Visual Analog Scale (VAS) ⁹⁴ ARVs dispensed Depression (Center for Epidemiological Studies-Depression Scale [CES-D])), Generalized Anxiety Disorder (GAD-7) ⁹⁶	B IQ PR IQ
Other measures			
Aims 1-4	Sociodemographics	Age, race/ethnicity, education, insurance, sex, gender	IQ
Aims 1-4	Pain characteristics	Brief Pain Inventory (BPI) Interference subscale ⁹⁰ Pain catastrophizing scale ⁹⁸ , Pain DETECT questionnaire ⁸⁴	IQ IQ
Aims 1-4	Pain treatment	Pain treatment (SSRIs, gabapentin, injections, physical therapy)	IQ/MR/PR
Aim 3	Substance use/disorder	Smoking (Fagerstrom test for nicotine dependence) ⁹⁹ , Alcohol Use Disorders Identification Test (AUDIT) ¹⁰⁰ , ASI ⁹⁷	IQ
Aim 3	HIV Risk Behaviors	HIV risk behaviors (HIV Risk-taking Behavior Scale ¹⁰¹⁻¹⁰³)	IQ
Aims 3, 4	Psychiatric symptoms	PTSD Checklist (PCL), ¹⁰⁴ Insomnia severity index, ¹⁰⁵	IQ
Aims 1, 3, 4	Quality of Life	Roland Morris Disability Questionnaire ¹⁰⁶ , Patient Reported Outcomes Quality of Life-HIV (PROQOL-HIV) ¹⁰⁷	IQ
Aims 1-4	Medical comorbidities	Comorbidities (obesity, cardiovascular disease, diabetes)	MR
Aims 1-4	Side effect vs benefit	Treatment Satisfaction Questionnaire for Medication (TSQM-9) ⁹¹	TQ
Aims 1-4	Urine cannabinoid	Urine GCMS for cannabinoids	

B=blood test; MR=Medical records; PR=Pharmacy records or Prescription Monitoring Program; IQ= in-person questionnaire; TQ=phone questionnaire; SSRI=selective serotonin reuptake inhibitor; TQ measures occur every week; IQ occurs at 0 and 14 weeks. B occurs at 0 at 14 weeks.

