Other key outcome variables will be alternative pain measures (painDETECT,⁸⁴ pain catastrophizing⁹⁸).

Other measures that have strong associations with medical cannabis use or neurologic pain will be measured, including biological sex, substance use, quality of life, HIV risk behaviors, symptoms of post-traumatic stress disorder (PTSD), insomnia and medical comorbidities (Table 8).

3) Study Population

3.A. Sample size and power

determination. For our primary analysis (Aim 1), we based our power analysis on proportion of participants with clinically significant change in BPI pain severity scale (30% reduction) in each condition.^{8,48} We will recruit 100 participants in total; we anticipate that approximately 50 will use high THC soft gel

capsules and 50 will use high CBD soft gel capsules. Conservatively assuming 15% attrition in each arm, 42 participants will be in each arm. Because the individual-level intra-class correlation coefficient (ICC) associated with change in pain severity over time is unknown, we conducted simulation studies with varying ICC values, i.e., 0.2, 0.3, and 0.4. We present power calculations for pain severity in Table 9. Based on prior studies,^{47,48} we predict that 40% of those using high THC capsules will experience clinically significant reduction in pain and 20% of those using high CBD capsules will experience clinically significant reduction in pain.¹¹⁰ We will have 84% power at a significance level of 5% (two-tailed test) to detect a 20% difference in proportion of participants who achieve clinically significant reduction in pain during the follow-up period between high THC soft-gel capsules (40%) and high CBD (20%) soft gel capsules. We will have greater power to detect a larger difference or when ICC is lower.

For analyses with continuous dependent variables (Aim 2-3), a sample size of 42 participants/arm will allow us to have >90% power to detect a moderate effect size (i.e., Cohen's $d=0.5$) under a more stringent condition (ICC=0.4). We will have greater power when the effect size is larger or when ICC is lower.

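### The adherence VAS is weekly in section 2.C but limited to weeks 0 and 14 in Table 8, and the power quoted for Aim 3 states neither the number of measurements nor the contrast

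*Combined protocol and SAP*

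**What the plan says.** Section 2.C, under adverse events (secondary outcomes), gives ARV adherence by the ACTG interview, with no frequency, and by the "Adherence Visual Analog Scale [VAS; weekly" item. The same sentence puts CES-D and GAD-7 at weeks 0 and 14, so frequency is set measure by measure. Section 2.C also describes the weekly phone or web contacts: "A total of 15 visits will occur, the first at baseline".

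The measures table (Table 8) has an adverse-events row that includes "AIDS Clinical Trial Group (ACTG Adherence) ⁹³ , Visual Analog Scale (VAS) ⁹⁴ ARVs dispensed". The row has four groups of measures (VL and CD4; ACTG and VAS; ARVs dispensed; CES-D and GAD-7) and four source codes in the order B, IQ, PR, IQ. Taken in order, ACTG and VAS share the first IQ. The footnote reads: "TQ measures occur every week; IQ occurs at 0 and 14 weeks".

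Section 3.A says of sample size: "Conservatively assuming 15% attrition in each arm, 42 participants will be in each arm". For the continuous outcomes of Aims 2-3 it says that "a sample size of 42 participants/arm will allow us to have >90% power to detect a moderate effect size", with Cohen's d of 0.5 and an ICC of 0.4, and adds that power is greater when the ICC is lower. Section 7.A analyses ARV adherence by mixed-effects linear regression under Aim 3.

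**The concern.** The text and the table give different collection schedules for the same measure. If the questionnaires are built from the table, the weekly VAS series is never collected. H4 names poorer ARV adherence as one of its outcomes, so this would remove most of the data on one component of a stated hypothesis.

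The choice also bears on power. A claim of more than 90% at d = 0.5 with 42 per arm is high for an outcome seen once or twice, but ordinary for one averaged over many weeks. The reader cannot tell from section 3.A which was assumed.

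**Working it through.** **Inputs.** From section 3.A: n = 42 per arm, d = 0.5, ICC ρ = 0.4. From section 2.C: 15 weekly assessments (baseline plus 14). From the Table 8 footnote: 2 assessments for an IQ item. Assumed, because not stated for Aims 2-3: two-sided 5% (section 3.A states this for Aim 1), equal correlation ρ between any two measurements, and d expressed in single-measurement SD units.

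**Method.** Write f for the variance of the analysed quantity relative to a single measurement. The effective standardised difference is δ = 0.5/√f, and power comes from the noncentral t with 82 df and noncentrality δ√(42/2).

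- Mean of m values: f = (1 + (m−1)ρ)/m
- Mean of k follow-up values adjusted for baseline: f = (1 + (k−1)ρ)/k − ρ²
- Mean of k follow-up values minus baseline: f = (1 + (k−1)ρ)/k + 1 − 2ρ

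**Step 1: reproduce the plan's figure.** For the 14 weekly follow-up values, f = (1 + 13×0.4)/14 = 6.2/14 = 0.443, δ = 0.751 and power is 92.5%. With all 15 values, f = 6.6/15 = 0.440, δ = 0.754 and power is 92.7%. The stated figure is therefore consistent with a mean over weekly values. At ρ = 0.4 at least 7 values are needed to pass 90%.

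Two further signs point the same way. The same weekly design-effect approach applied to Aim 1 (40% v 20%) gives 97.9%, 92.7% and 85.8% at ICC 0.2, 0.3 and 0.4, close to the 97%, 91% and 84% in Table 9. And section 3.A says that power rises as ICC falls, which is true of a mean over repeated values. For simple two-visit change, f = 2(1 − ρ), so power would move the other way.

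**Step 2: compare the schedules like for like at ICC 0.4.**

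| Contrast | Weekly: f, δ, power | Weeks 0 and 14: f, δ, power |
|---|---|---|
| Mean of all values | 0.440, 0.754, 92.7% | (1 + 0.4)/2 = 0.700, 0.598, 77.2% |
| Baseline-adjusted | 0.443 − 0.16 = 0.283, 0.940, 98.9% | 1 − 0.16 = 0.840, 0.546, 69.5% |
| Change from baseline | 0.443 + 1 − 0.8 = 0.643, 0.624, 80.6% | 1 + 1 − 0.8 = 1.200, 0.456, 54.3% |

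Week 14 alone (f = 1) gives 62.0%. The mean of both visits is the most favourable two-visit reading, because it treats baseline as an outcome and supposes the full difference is already present there.

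**Step 3: can other settings rescue two visits?** By the normal approximation, the mean of both visits reaches 81.1% at ICC 0.3, 84.1% at ICC 0.2 and 89.98% at ICC 0. At ICC 0.4 it reaches 86.3% with a one-sided 5% test and 84.8% with 50 per arm and no attrition. No single one of these changes takes it past 90%. At ICC 0.4, 90% power from two visits would need about 59 per arm (mean of both), 71 (baseline-adjusted) or 101 (change).

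**The case against.** The strongest reply is that section 2.C is specific and deliberate: it marks the VAS weekly and the psychological scales at weeks 0 and 14 in one sentence. In Table 8, ACTG and VAS share one entry and one code, which may describe only the ACTG interview, and the alignment of codes to measures is inferred from their order in extracted text. The weekly series is lost only if staff follow the table. That stands as a reason to resolve the conflict towards weekly collection, but it does not remove the conflict. Four groups match four codes in order, B fits the blood tests and PR fits dispensed ARVs, and other weekly items in the table, such as BPI severity, do carry TQ.

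Three stronger readings are tempting, and the documents do not support them.

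- A reader might take section 3.C as confirming that adherence is asked by phone. Its list of questionnaire topics does not separate phone from in-person contacts, and it also includes psychological symptoms, whose CES-D and GAD-7 scales are given only at weeks 0 and 14.
- A reader might infer that weekly collection secures the 90%. It does not for simple change from baseline, which reaches about 81%. Nor is it fair to set 93% for a weekly mean against 54% to 70% for two-visit change or baseline-adjusted contrasts, since these are different quantities.
- A reader might equate the VAS with adherence as a whole. The ACTG interview is IQ in Table 8 whatever code the VAS receives.

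It is also fair to object that section 3.A states neither the number of measurements nor the contrast, and introduces the ICC for change in pain severity, not adherence. The recomputed figures are therefore conditional.

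**Conclusion.** The schedule conflict is real and the two places must be reconciled. On the plan's own n, d and ICC, with equal correlation and two-sided 5% assumed, weekly collection adds about 15 to 29 percentage points of power within a given contrast (92.7 − 77.2 = 15.5; 98.9 − 69.5 = 29.4; 80.6 − 54.3 = 26.3). With two visits, none of the contrasts examined reaches the stated 90%; they run from about 54% to 77%. With weekly data the claim is met for the mean or the baseline-adjusted contrast, but not for simple change.

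This does not show that the stated figure is a miscalculation. It shows that the figure cannot be applied to adherence until the schedule and contrast are fixed. Because the outcome is secondary and the repair small, this is a worthwhile correction and not a threat to the primary analysis. CES-D, GAD-7, VL and the cytokines are also two-time-point outcomes under the same power sentence, so the need to state measurements and contrast is not confined to adherence.

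**What to change.** 1. In Table 8, split the shared entry: code the VAS as TQ (weekly), to match section 2.C, and leave the ACTG interview as IQ.
2. In section 7.A, Aim 3, specify that the weekly follow-up VAS values enter the mixed model with baseline VAS as a covariate.
3. In section 3.A, state the number of measurements and the contrast behind the claim of more than 90%.
4. For any adherence measure taken only at weeks 0 and 14 (the ACTG interview, and the VAS if it is in fact collected twice), restate the power as about 54-77% at d = 0.5 and ICC 0.4, naming the contrast used.

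The cost is one split table entry and a few sentences. The weekly contact already exists. The documents do not say whether the VAS item is already counted in the planned 5-7 minute questionnaire, so that should be confirmed. If it is not, one short item is added each week. The change should be made before questionnaires are built or, if data collection has begun, after checking which schedule has been followed.

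### The power above 90% stated for Aims 2-3 is not reached for outcomes measured only at weeks 0 and 14; between-arm tests have about 54% to 77%

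*Combined protocol and SAP*

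**What the plan says.** Section 3.A gives one power statement for the continuous outcomes of Aims 2-3: "a sample size of 42 participants/arm will allow us to have >90% power to detect a moderate effect size", namely Cohen's d of 0.5, "under a more stringent condition (ICC=0.4"). It adds: "We will have greater power when the effect size is larger or when ICC is lower". It does not name the tested term, the SD that standardises d, or the number of measurements per participant.

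The ICC enters the same section only for the primary outcome: "Because the individual-level intra-class correlation coefficient (ICC) associated with change in pain severity over time is unknown", values of 0.2, 0.3 and 0.4 were simulated. The two-sided 5% level is likewise stated only for Aim 1.

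The schedule is clear for most of these outcomes. The footnote to the measures table reads "IQ occurs at 0 and 14 weeks. B occurs at 0 at 14 weeks". Section 2.C agrees: "Blood draws will occur at week 0 and 14 in-person visits", which covers cytokines and viral load. For the psychological scales it gives "depression (CES-D; 0 and 14 weeks") and the same two visits for GAD-7.

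Section 7.A specifies mixed-effects linear models. For Aim 2 it lists arm, time and arm-by-time terms; for Aim 3 it names no tested term. H2, H3 and H4 all compare high THC with high CBD products.

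**The concern.** Power above 90% for d=0.5 with 42 per arm is more than a single between-arm comparison can give, so it must rely on repeated measurements. Most of the outcomes it covers have only two, one of them at baseline.

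The ICC remark raises a related doubt. A lower within-person correlation helps when visits are averaged, but it hurts when the test is on change from baseline. H2 and H3 are about change.

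The risk lies in interpretation. H4 concerns psychological symptoms, adherence and viral load. A null result believed to carry more than 90% power could be taken as evidence of no difference that the data cannot support.

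**Working it through.** **Inputs.** From section 3.A: n=42 per arm, d=0.5, ICC=0.4. From section 2.C and the measures table: two measurements, weeks 0 and 14. Two assumptions are needed: the ICC is the week 0 to week 14 correlation r, and the two-sided 5% level of Aim 1 also applies here. Power is from the noncentral t with 82 df (81 when adjusting for baseline). With effective standardised difference D, the noncentrality is D × √(42/2) = 4.583 × D.

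**Looking for the plan's figure.** For the mean of m measures, D = d × √(m / (1 + (m−1) × ICC)). At ICC 0.4:

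| m | Power |
|---|---|
| 2 | 77.2% |
| 6 | 89.3% |
| 7 | 90.1% |
| 14 | 92.5% |
| 15 | 92.7% |

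The stated figure therefore appears only with about 7 or more averaged measures. A weekly schedule would produce it. That this is where it came from is an inference, and the shortfall does not depend on it.

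**Two visits, r=0.4.**

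- Arm-by-time, d on the outcome SD: D = 0.5/√(2(1−0.4)) = 0.5/1.095 = 0.456; noncentrality 2.09; power 54.3%.
- Week 14 alone, or d on the SD of change: D = 0.5; noncentrality 2.29; power 62.0%.
- Baseline-adjusted, arms balanced at baseline: D = 0.5/√(1−0.16) = 0.546; noncentrality 2.50; power 69.5%.
- Arm effect averaged over both visits: D = 0.5 × √(2/1.4) = 0.598; noncentrality 2.74; power 77.2%. This requires the arms to differ by 0.5 at week 0 as well. If they differ only at week 14, D is halved and power is 27.2%.

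A simulation of 40,000 runs gave 54.2%, 61.9%, 69.0% and 77.3%, and 27.2% for the week-14-only case.

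**Direction of the ICC effect.**

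| Test | r=0.2 | r=0.3 | r=0.4 | r=0.7 |
|---|---|---|---|---|
| Arm-by-time, outcome SD | 43.3% | 48.2% | 54.3% | 83.2% |
| Week 14 alone, or SD of change | 62.0% | 62.0% | 62.0% | 62.0% |
| Baseline-adjusted | 63.7% | 66.0% | 69.5% | 88.7% |
| Two-visit average | 83.2% | 80.2% | 77.2% | 69.0% |

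The plan's remark holds in the last row only. In the first and third rows 0.4 is the most favourable of the plan's three values.

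**How far inputs must move to reach 90%.** Arm-by-time on the outcome SD needs r of about 0.76, and the baseline-adjusted test about 0.72. The two-visit average gives 89.3% even at r=0. At r=0.4, in the order of the table:

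- a one-sided 5% test gives 67%, 73%, 80% and 86%;
- 50 per arm with no attrition gives 62%, 70%, 77% and 84%;
- the d detectable with 90% power at 42 per arm is 0.78, 0.72, 0.66 and 0.60.

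**The case against.** The strongest reply is that the sentence is under-specified rather than wrong. It names no term, SD or number of visits, and the ICC and test level are borrowed from Aim 1, so the percentages are scenario values. That stands as a caution about any single figure. It does not rescue the claim, because every between-arm two-visit reading at the stated inputs falls short. Reaching 90% takes changes to stated inputs together, such as a one-sided test with 50 per arm (91% for the two-visit average).

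Second, Aim 2 also lists a time effect. Pooled over 84 participants it has 98.5% power at r=0.4 with d on the outcome SD. This is true, but it describes change in the whole cohort and does not test H2 to H4.

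Third, 54% to 77% is not a hard range. Scaling d to the within-person SD would put arm-by-time at about 36%. The 77% presumes a week-0 difference, which suits hypotheses about change poorly. Both points are right, and both enlarge the shortfall. The figures most relevant to H2 and H3 are 54% and 62%.

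Fourth, neither a baseline-adjusted nor a week-14-only test is named for these outcomes. They are shown here because Aim 3 leaves its term open and because they are more favourable than the 54% case, yet still below 90%.

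**Conclusion.** The concern holds. For outcomes measured at weeks 0 and 14, the stated power above 90% is not reached by any between-arm test at the plan's own n, d and ICC. The arm-by-time test named for Aim 2 has 54% power (d on the outcome SD) or 62% (d on the SD of change), and the most favourable two-visit test has 77%. A true difference of d=0.5 would be missed about 23% to 46% of the time, against under 10% as stated. The ICC remark is reversed for arm-by-time on the outcome SD and for a baseline-adjusted test, has no bearing on week 14 alone or d on the SD of change, and is correct for a visit average.

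The figures rest on reading the ICC as the week 0 to week 14 correlation and on a two-sided 5% test. The conclusion survives correlations across the plan's 0.2 to 0.4. At a correlation of 0.4 it also survives a one-sided test or full retention, each taken alone. These are secondary outcomes and the sample size rests on Aim 1, so this corrects a power statement and does not challenge the sample size. It should be fixed.

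**What to change.** Restate the power in section 3.A for week 0/14 outcomes, naming the tested term, the SD behind d, the number of measurements and the assumed correlation. Suggested wording: *For outcomes measured at weeks 0 and 14, 42 participants per arm give about 54% power (two-sided 5%) for the Aim 2 arm-by-time test with d=0.5 on the outcome SD and a week 0 to week 14 correlation of 0.4 (43% at 0.2, 83% at 0.7); 90% power is reached at d of about 0.78.* If d is meant on the SD of change, the figures are 62% and about 0.72.

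For Aim 3, name the tested term in section 7.A first, then give the matching figure.

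For arm-by-time with d on the outcome SD, and for a baseline-adjusted test if one is adopted, say that power falls as the correlation falls and stop calling 0.4 the stringent case. Keep the present ICC sentence for visit averages only.

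Keep the figure above 90% only for an outcome collected weekly and analysed as a visit average (14 visits: 92.5% at ICC 0.4). The adherence VAS could qualify, but section 2.C has it weekly while the measures table, read in cell order, lists it with the in-person questionnaires; the two need reconciling.

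The cost is wording, a named term for Aim 3, one schedule reconciliation and a less favourable stated power. No extra participants and no change to the planned models are needed.
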